That population will yield a subset with advancing but asymptomatic disease. Within that sub-population a group will exist who will proceed to diagnosis and be willing to learn about clinical trials. By measuring this response the effectiveness of the messaging about engaging diagnosis and follow up can be shown. There is not comparable data so this will establish a baseline.

A separate track will be to measure the number of participants who enter the diet and lifestyle education programs. Measuring this response will also establish a baseline measure for the effectiveness of this messaging and inform future efforts.

Overview

Research has shown that there is a high incidence of undiagnosed fibrosis within comorbid populations as a result of the frequently asymptomatic course of NASH

development. (<https://www.ncbi.nlm.nih.gov/pmc/articles/PMC4542082/>)
Liver disease is a dangerous and expensive problem to manage medically with the cost of NAFLD estimated to exceed \$32 billion per year.

(<https://www.sciencedaily.com/releases/2018/07/180703105956.htm>)

Liver disease in the form of Nonalcoholic fatty liver disease (NAFLD) and nonalcoholic steatohepatitis (NASH) are rapidly increasing population health threats driven primarily by diet and lifestyle. Fibrotic liver disease, culminating in cirrhosis, is frequently asymptomatic so it is common for a patient to first learn of what is a life threatening condition by being told that they have cirrhosis. Management and treatment of cirrhosis is complex and very costly with few treatment options and the only current therapy being a very expensive transplant for end stage liver disease.

The position of the Fatty Liver Foundation is that this problem is magnified by the current American Association for the Study of Liver Disease, (AASLD), practice guidelines which do not advise routine screening for NAFLD. This is the policy:

Excerpts from the AASLD Practice Guidelines 2017:

(AASLD Diagnosis Mgt NAFLD Chalasani et al 2017 Hepatology)

- It can be argued that there should be systematic screening for nonalcoholic fatty liver disease, (NAFLD), at least among higher-risk individuals attending diabetes and obesity clinics.

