FibroScan is available and has been shown to detect advancing levels of fibrosis, and it is clear that nonalcoholic fatty liver disease is increasing in prevalence throughout the western and developing worlds. Advancing liver disease leads to fibrosis, cirrhosis, and early death in a substantial portion of the population who could be helped with earlier lifestyle and medical interventions.

Vibrationcontrolled transient elastography (VCTE) is a point-of-service non-invasive technology that measures tissue elasticity and steatosis and can identify individuals at risk for disease progression and may therefore serve as an effective screening tool to alter the natural history of this disease and improve outcomes.

Changing a foundational strategy, such as responding to symptoms of liver disease, which is the current recommendation, to one of proactively intervening by screening for asymptomatic disease carries a large cost burden and is difficult to accomplish.

Objectives

The goal of this screening study is to gather FibroScan data from the at-risk but undiagnosed population on a self-selection basis so that perceived incidence rates can be calculated and the economics of a single function screening service can be evaluated.

The objective is to develop evidence based information to determine if noninvasive screening of at risk, comorbid people is feasible with this modality.

Furthermore, a secondary objective is to educate all participants about liver disease, lifestyle, healthy diets, and the role of clinical trials as part of the Foundation's larger mission of being patient advocates.

The value and necessity of clinical trials for the development of effective therapies is not well understood by the public. A goal of the foundation is to provide information about the clinical trial process to screening participants. The information is of a general nature (examples are attached). No specific trials will be mentioned. The participants will also be offered the opportunity to receive additional general education about trials and provided with links to systems in which they can explore available trials should they wish to do so. That information is of a general nature and no specific trials will be promoted. Participation in the screening will not automatically enroll them in further education as that decision is post testing and opt-in.

Questions Posed by this Study:

- What population demographics justify routine screening on a cost benefit basis?

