- The de-identified, but self-described, chronic ailments will be used with the scan results to broadly identify cohorts that may benefit from screening for asymptomatic disease.
- What operating cost burden is required to sustain a mobile screening project and what is the minimum utilization required to justify it?
- The operating costs of the study will be captured in order to inform an analysis of the financial constraints for deployment of mobile screening systems into local underserved communities.
- What portion of the asymptomatic patients with advanced disease will be willing to learn about clinical trials?
- Analysis of the posttest behavior of participants by their enrolling to learn more about clinical trials will measure the efficacy of using this method to educate the at risk population about clinical trials and ultimately inform decisions about how trial participants may be recruited in the future.
- What portion of the patients take advantage of free online diet support?
- Lifestyle changes are challenging as it is difficult to engage patients in the weeks following any testing. Tracking of the number who take advantage of the follow-up support will help guide future efforts to develop educational materials.

Patient Selection Criteria

The screening will be available to adults who self-select and who meet the inclusion criteria. The project will stop at 3 months or 1,000 patients, whichever occurs first. The goal is to

examine whether a self-referral design can serve as a cost effective patient centered wellness screening model.

Who may participate

- Adults 18 and over
- Patients with no diagnosis of liver disease
- Patients with any of these self-identified chronic conditions
 - Type 2 diabetes
 - Metabolic syndrome
 - Cardiovascular disease
 - Pre Diabetes
 - Sleep apnea
 - Digestive disorders
 - Osteoporosis
 - Polycystic ovarian syndrome
 - Psoriasis

Who may not participate

- Age less than 18
- Pregnant women
- Anyone with an implanted electronic device such as a defibrillator
- Morbidly obese, BMI 40 or greater
- Anyone not personally able to give informed consent
 - Non English speakers, no translator is available

Trial Candidate Outreach

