Patients will also be told about clinical trials and receive information about that process and offered access to online educational information and trial access tools if they are interested. Part of the outreach from the study is to educate patients about the need for clinical trials and to encourage learning more about it. The core message is that therapies will not be successful in the future without a cohort of patients who have been educated about clinical trials and are willing to consider participating. We will not recruit for any particular trials but will discuss their value and importance to society and potentially to individual patients.

By focusing on asymptomatic and undiagnosed liver disease the project will identify a currently unavailable population ideally suited for the upcoming clinical trials required for the development of therapies for liver fibrosis in NAFLD, NASH, and cirrhosis.

Study procedures

Testing will be done by appointment. Since the test itself is very fast, with a planned test throughput of 15 minutes, most of the visit will be taken up by the consent procedure, explanation of the test itself, discussion of liver disease, and distribution of literature.

When the test schedule is created, patients will be instructed not to eat within 3 hours of their appointment time so that a convenient time can be chosen.

There will be four steps in the process.

Step 1: Explanation and Consent

- At the intake point a staff members will explain the purpose for the study, provide information about liver disease, fatty liver, NASH, and fibrosis.
- The staff member will review the inclusion/exclusion rules and confirm that the patient has met the 3 hour fasting rule and has not been diagnosed with a liver disease.
- If inclusion criteria are met, the staff member will describe non-invasive testing process using the FibroScan, give the patient printed information, and explain that it measures both liver stiffness and fat content which their doctor can use to help them with any diagnosis that may be needed. It will be explained that FibroScan does not provide a diagnosis but is part of the information a doctor would use to understand the health of their liver. A sample test report will be used as a visual aid. Any questions will be answered.

- The staff member will explain what information will be gathered and explain that it is demographic information only and that no personally identifiable information will be collected.

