- When any questions have been answered, the staff member will explain consent, provide the patient with the document, and answer any other questions.
- Upon signing of the consent the staff member will assign a random number to the consent and to the patient questionnaire.

Step 2: Data Capture

- After signing the consent form the patient will be asked to fill out the demographic form which will record basic health information, height, weight, sex, age, ethnicity, and identify any comorbid conditions of which they are aware from a list of common liver related comorbidities.

Step 3: The FibroScan test

- The patient will take the completed intake form and the educational materials with them to the FibroScan test room where the test will be performed.
- A certified FibroScan technician will double check the intake form and answer any additional questions that the patient may have.
- The technician will then administer the test according to the established standard test procedure and will identify it with the random number assigned to this test in step 1.

Step 4: Posttest process and instructions

- When the test is complete the test results will be printed out and given to the patient.
- The patient will also be given detailed information about how FibroScan is used and what it measures in a format that they can use to inform themselves so that they can better discuss the results and next steps with a physician. This will include explanations of how liver stiffness and fatty infiltration are defined and measured by the device.
- The patient will be asked to assess their perception of the value of the test to them personally by indicating what they perceive the value is of the test to them personally on a scale from nothing to over \$400.
- The patient will also be given printed information providing ways to contact resources and information about lifestyle changes, free support services, and information about how to access additional online tools.
- Most importantly, the patient will be instructed on how to access telemedicine support for interpretation of the test results and next steps. The technician will explain that the study provides the test, but interpretation must be done by a physician. Some patients may elect to discuss it with their existing doctor but

they will be encouraged to utilize the hepatology services, particularly if their test results are elevated.

Confidentiality

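### Two of the protocol's own questions are only partly answered: trial interest is not reported by fibrosis stage, and the itemised forms have no entry for four of the nine qualifying conditions

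*Combined protocol and SAP*

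**What the plan says.** **Trial interest.** The protocol section Questions Posed by this Study asks "What portion of the asymptomatic patients with advanced disease will be willing to learn about clinical trials". The Hypothesis section sets the same denominator, people whose disease is progressing without symptoms: "Within that sub-population a group will exist who will proceed to diagnosis and be willing to learn about clinical trials". The measure named for this question is behaviour: "Analysis of the posttest behavior of participants by their enrolling to learn more about clinical trials". Intended Use of the Data says this response is tracked in aggregate, and the note in SAP Data Analysis rules out individual follow-up. Separately, the post-test Experience and Satisfaction Survey asks each subject, on a five-point scale, how likely they are to seek information about trials. SAP Data Analysis treats that item as exploratory and plans answer frequencies only.

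**Cohorts.** The same protocol section asks "What population demographics justify routine screening on a cost benefit basis" and says that "chronic ailments will be used with the scan results to broadly identify cohorts that may benefit from screening". Who may participate lists nine qualifying conditions, among them "Polycystic ovarian syndrome". SAP Data Collection names the patient-completed forms as the source of data for analysis and itemises them. Step 2 (Data Capture) also mentions a list of liver-related comorbidities without giving its contents. At Step 1, "The staff member will review the inclusion/exclusion rules and confirm that the patient has met the 3 hour fasting rule", but nothing says that the qualifying condition is written down.

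**The concern.** The first question is a proportion within a subgroup, and the plan produces a proportion over everyone. The second is to be approached by splitting scan results by ailment, and the itemised forms do not carry every ailment that makes a person eligible.

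Both gaps have to be closed before data capture. Participants are anonymous and not followed up, so a survey without the study ID could not be matched to a scan later, and a condition not recorded at intake could not be recovered. The report would then lack trial interest for the group named in the hypothesis. A person admitted only for, say, sleep apnea could appear in the data with no qualifying condition. Scan yield by cohort is only one input to the cost-benefit question; the cost analysis itself is outside this point.

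**Working it through.** **The plan's own figure.** The only sample-size statement is a minimum of 400 for power of around 0.8, with a maximum of 1,000. No effect size, rate or comparison is given, so it cannot be reproduced. It is not disputed here; 400 and 1,000 serve only as denominators.

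**1. Does any planned output give trial interest in advanced disease?**
- Online enrolment: aggregate, so not split by stage.
- Survey item: overall frequency only.
- SAP primary goal: fat and stiffness categories in men and women; trial interest is not used.
- SAP secondary goal: factors associated with fat, with or without stiffness; trial interest is not used.

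None does.

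**2. Could the overall frequency stand in?** Pooled interest = a × p(advanced) + (1 − a) × p(rest), where a is the advanced share. The documents give none of these, so assume p(rest) = 50%.
- a = 10%: 0.10 × 0.30 + 0.90 × 0.50 = 48%; 0.10 × 0.90 + 0.90 × 0.50 = 54%.
- a = 5%: 0.05 × 0.30 + 0.95 × 0.50 = 49%; 0.05 × 0.90 + 0.95 × 0.50 = 52%.

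A swing from 30% to 90% in the group of interest moves the pooled figure by 6 or 3 percentage points. It cannot stand in.

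**3. What precision would a table by stage give?** At an observed 50%, the Wilson 95% interval is 0.5 ± 0.5z/√(n + z²), with z = 1.96. Assume 2%, 5% or 10% advanced among 400 or 1,000 participants, all of whom answer the survey.

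| Advanced cases | From | 95% interval |
|---|---|---|
| 8 | 2% of 400 | 21.5%-78.5% |
| 20 | 5% of 400, or 2% of 1,000 | 29.9%-70.1% |
| 40 | 10% of 400 | 35.2%-64.8% |
| 50 | 5% of 1,000 | 36.6%-63.4% |
| 100 | 10% of 1,000 | 40.4%-59.6% |

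Exact intervals are somewhat wider at the small end (16%-84% at 8 cases). Enrolment also stops at 3 months, so 400 is a target and not a guaranteed floor.

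**4. What would the table need?**
- Linkage. Staff "will assign a random number to the consent and to the patient questionnaire", and the scan carries the same number. The Confidentiality section places the code on the consent and demographic forms. The post-test survey is not named, and the SAP worksheet numbers subjects sequentially with no stated mapping.
- A definition of advanced disease. None is given. The transient elastography table prints F4 as ≤ 14.0 kPa with no stage above it, while the SAP primary goal has a category for stiffness in the cirrhosis range.
- Clarity on what participants know when surveyed. The reporting and survey sections have a hepatologist determine stage and subjects answer after hearing their results. Outputs of the project for the patient and Step 4 say that the study does not interpret results.

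**5. Qualifying conditions against the itemised forms.**

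| Qualifying condition | Item on the forms |
|---|---|
| Type 2 diabetes | Diabetes mellitus, type not separated |
| Metabolic syndrome | By components |
| Cardiovascular disease | Heart disease, heart attack, arrhythmia, stroke |
| Osteoporosis | Pooled with osteopenia |
| Digestive disorders | Mainly inflammatory bowel disease (stomach and colon appear only under cancer) |
| Pre-diabetes | None |
| Sleep apnea | None |
| Polycystic ovarian syndrome | None |
| Psoriasis | None |

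Five of nine have a full or partial item; four have none.

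**The case against.** The strongest case against is that the trial-interest question is exploratory and names enrolment as its measure. Enrolment is kept aggregate because of the anonymity design. A survey table would show stated intention, so the named measure would stay unanswered by stage even after the fix. This stands, and the table must be labelled accordingly. It is still the only individual-level information on trial interest that the study collects.

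Second, the protocol promises only to identify cohorts broadly and does not say that each inclusion condition is an analysis cohort. The unitemised intake list may also hold the missing conditions. This stands too, and it makes the consequence of the second part conditional.

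Three stronger readings are tempting, and the documents do not support them:
- A reader might infer that the plan rules out a table by stage. It does not. Intended Use of the Data foresees aggregate subtotals, and the SAP's statement that these data get no statistical analysis does not bar a descriptive cross-tabulation. The numbered questionnaire and single worksheet suggest that linkage may be intended.
- A reader might infer that readings above 14.0 kPa would be lost from the advanced group. That is one literal reading of the table. The SAP's cirrhosis category points the other way, and no exclusion rule is written.
- A reader might infer that a certain number of advanced cases makes the table adequate. The documents supply no precision target, so no threshold is claimed.

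**Conclusion.** Both mismatches are in the text, and confidence in them is high. The plan has no output for trial interest in advanced disease, and four of the nine qualifying conditions have no entry on the itemised forms. The changes should be made, because the information may be irrecoverable once anonymous data capture has begun.

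The size is less certain. The precision range above rests on assumed shares of 2% to 10%, full survey response and 50% interest. The share of participants who qualify only through an uncovered condition is not given, and whether those cohorts are lost depends on the unseen intake list. It would be wrong to infer that the main result is compromised: the primary prevalence estimate does not depend on either gap. The defect in the elastography table bears on staging generally and deserves separate treatment.

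**What to change.** **Trial interest**
1. State that the post-test survey carries the random study ID, and how that ID maps to the worksheet number.
2. Reconcile the elastography table with the SAP's cirrhosis category so that every reading has a stage, then define advanced disease. No cut-off is proposed here.
3. Reconcile the sections on whether results have been explained when the survey is completed.
4. Add one descriptive SAP table of the trial-information item by stage: all five answers, with a 95% interval for likely or very likely. Label it as stated intention, and say that enrolment remains unlinked to stage.

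**Cohorts**
1. Check the intake comorbidity list against the inclusion list. Unless they are already there, add YES/NO items for pre-diabetes, sleep apnea, polycystic ovarian syndrome, psoriasis and other digestive disorders.
2. Tabulate the primary fat and stiffness categories by qualifying condition.

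The cost is at most about five tick-boxes, a few sentences of text and two descriptive tables. The form becomes slightly longer. No identifying data and no added procedure are needed.

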The primary patient outreach efforts will be to focus on high risk comorbid patients. We will communicate with local physicians to inform them that the service exists and invite them to refer appropriate patients to the screening facility or alternatively invite us to visit their offices with a portable unit.

The Foundation will also perform educational outreach through social media, communication through internet advertising, online forums, interaction with local support groups, media interviews and other educational efforts emphasizing the problem of our growing societal health crisis with obesity in general and liver disease in particular.

It is important to emphasize that during this study the FibroScan test will be free to qualified patients but they will be interviewed to ask what price they would be willing to pay on a private pay basis. This information will be used to perform the analysis of the viability of a private pay model. There will be no insurance or third party payment. Following testing the patient will be asked what payment amount, ranging from zero to more than \$400, would seem fair to them as a charge. The goal is to develop perceived value measures which can inform the financial modeling for the development of the fully deployed business plan.

Outputs of the project for the patient

All patients will receive education about liver disease as part of the intake process. Following the test, the patient will receive a printed output from their FibroScan test and instructions about next steps. Interpretation of test results require professional medical knowledge which is not provided by the study. Patients will be directed to a telemedicine system where they can discuss their results with professional staff and determine any next steps. Patients may elect to confer with their personal physician instead as is their right. Patients with test results indicating no active disease will be offered connections to nutrition and dietary support. In all cases patients will be offered enrollment in online educational tools about diet and lifestyle.

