Subjects will be asked to complete a survey about their experience after having the CAP-FibroScan and hearing their results, using a 5-point scale: very likely—likely—neither likely nor unlikely—unlikely—very unlikely.

1. Having completed the CAP-FibroScan and obtained your results, how likely are you to:
 - recommend this test to a friend or family member?
 - share your results with your doctor?
 - consult with a liver specialist?
 - seek information about FDA-approved clinical trials of therapies for non-alcoholic fatty liver disease?

Subjects will be asked to assess their level of satisfaction with the CAP-FibroScan procedure after being informed of their results, using a 5-point scale: very satisfied—satisfied—neither satisfied nor dissatisfied—dissatisfied—very dissatisfied.

2. Having had the CAP-FibroScan and obtained your results, how satisfied are you with the procedure?
 - a. If you answered very satisfied or satisfied, please check all the reasons for your answer:

- Ease of scheduling appointment for procedure.
 - Scheduled procedure occurred on time.
 - Cleanliness of the facility.
 - Professionalism and friendliness of staff.
 - Understandable explanation of the procedure and sufficient answers to my questions.
 - Quality of explanation of the results and quality of the answers to your questions about the results.
 - Comprehensive discussion of options my future care.
- b. If you answered dissatisfied or very dissatisfied, please check all the reasons for your answer:
- Lack of ease of scheduling appointment for procedure.
 - Procedure did not occur on time.
 - Problems with the cleanliness of the facility.
 - Problems with the professionalism or friendliness of staff.
 - Inadequate explanation of the procedure and deficient answers to my questions.
 - Inadequate explanation of the results and deficient answers to my questions about the results.
 - Inadequate discussion of options for my future care.
3. Having had the CAP-FibroScan and obtained your results, how satisfied are you that the procedure provided useful information about your health?
- a. If you answered very satisfied or satisfied, please check all the reasons for your answer:
- I understand what the CAP-FibroScan measures.
 - I understand how much fat I have within my liver.
 - I understand if I have or do not have evidence of scarring (fibrosis) of my liver.
 - The results gave me a better understanding of my liver health.

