 - No fat but evidence of liver stiffness
 - Fat without liver stiffness
 - Fat with liver stiffness
 - Stiffness values indicative of cirrhosis
 - Stiffness values indicative of fibrosis without cirrhosis

NOTE: no individual follow up or track will be done as not personally identifiable information will be captured or retained.

2. The secondary goal is to determine factors that are statistically significantly associated with the presence or absence of fat with or without increased liver stiffness.

We will analyze data using a standard statistical software package, Stata® 12.1 (Stata Corp, College Station, TX). We will express continuous variables using the mean ± standard deviation, and we will test the null-hypothesis using the Student t-test. We will compare categorical variables using contingency table analysis. For all statistical tests, we will define a two-sided p-value of ≤0.05 as statistically significant. We will perform multivariate analysis of all risk factors found to be statically significant (p ≤0.05) using univariate analysis.

This exploratory goal seeks to determine the degree of satisfaction of subjects who undergo a screening CAP-FibroScan free of charge.

We will calculate the frequency of answers for each of the five items reflecting subjects' likelihood of:

- recommending this test to a friend or family member.
- sharing their results with their doctor.
- consulting with a liver specialist.
- seeking information about FDA-approved clinical trials of therapies for non-alcoholic fatty liver disease.
-

We will not perform statistical analyses for these descriptive data.

Disease Staging

The disease staging to be analyzed will be based upon these breakpoints from the FibroScan test. The test scores will be translated into these staging ranges for analysis.

Transient Elastography (TE):

Disease	F0-F1	F2	F3	F4
NAFLD/NASH	≤ 7.0	≤ 7.5	≤ 10.0	≤ 14.0

Reference: Current Gastroenterology Reports. 2014; 16: 372

TE Interpretation: The subject's liver stiffness score in kPa units shows:

- **F0:** No liver fibrosis
- **F1-2:** Mild-Moderate liver fibrosis
- **F3:** Severe liver fibrosis
- **F4:** Cirrhosis

Controlled Attenuation Parameter:

Steatosis Grade	% Steatosis on Liver Biopsy	CAP Value
Mild (S1)	5-33%	225-275 dB/M
Moderate (S2) to Severe (S3)	>33% >66%	275-400 dB/M

Reference: World J Gastroenterol. 2016; 22: 7236

DATA COLLECTION

Demographics:

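### Sign-ups and interest recorded only after the visit give a post-visit level, not the efficacy or effectiveness of the education, and the sign-up count is not tied to screened participants or to disease stage

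*Combined protocol and SAP*

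**What the plan says.** Three statements in the protocol give the post-visit response an effect reading:

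- Questions Posed by this Study: analysis of who enrols after the test to learn about trials "will measure the efficacy of using this method to educate the at risk population about clinical trials". The result is also meant to guide future trial recruitment. The question above it concerns symptom-free patients with advanced disease.
- Hypothesis, on proceeding to diagnosis and learning about trials: "By measuring this response the effectiveness of the messaging about engaging diagnosis and follow up can be shown". The next sentence reads "There is not comparable data so this will establish a baseline".
- Hypothesis, on entry to the diet and lifestyle programmes: "Measuring this response will also establish a baseline measure for the effectiveness of this messaging and inform future efforts".

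On measurement:

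- Objectives and Outputs of the project for the patient: all participants are educated. Enrolment in further education is opt-in and follows the test.
- Experience and Satisfaction Survey: "Subjects will be asked to complete a survey about their experience after having the CAP-FibroScan and hearing their results". One item asks how likely the person is to look for trial information.
- Step 2 and both Data Collection sections: no listed intake item asks about prior interest in trials or diet support.
- Intended Use of the Data: the response to online trial and diet information is followed in aggregate only. The note in the SAP's Data Analysis section rules out individual tracking.
- Confidentiality: the random code joins consent form, demographic form and scan. Online enrolment is not mentioned.
- Trial Candidate Outreach: "The Foundation will also perform educational outreach through social media, communication through internet advertising, online forums", among other public channels.
- SAP, Data Analysis: the likelihood items are reported as frequencies without testing. No analysis of online enrolment is given.

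**The concern.** An effect needs two quantities: the response with the education, and the response the same people would have given without it. The plan records only the first. The SAP describes the participants as self-selected and health-minded, so many may already be interested in trials or diet support before the visit. With a single post-visit figure, that prior interest is credited to the education.

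The uptake share has a second weakness. Its denominator, the number screened, is known. Its numerator is an aggregate count for which the plan states no rule on who is counted, how repeat sign-ups are removed, or how sign-ups are assigned to a disease stage.

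At stake is an educational question, but one meant to inform recruitment strategy and later programmes. A figure reported as efficacy could be used to justify this method of education when it may reflect only who chose to come. Prior interest that was not asked about before the visit cannot be recovered afterwards.

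**Working it through.** **Inputs.** From the documents: a minimum of 400 and a maximum of 1,000 participants, and power of around 0.8 (Intended Use of the Data); two-sided 0.05 (SAP). All rates and counts below other than these are assumptions for illustration.

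**1. The plan's own figure.** No figure is given for the education effect. The 400 at power 0.8 comes without effect size, rate or hypothesis, so it cannot be reproduced. Solving backwards for a one-sample test: (1.960 + 0.842)/√400 = 0.140 SD, which is 0.140 × 0.5 = 7.0 points around 50%. Nothing ties this to the education question.

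**2. What one post-visit value says about an effect.** Effect = post − reference, where the reference (interest beforehand, or enrolment without the education) is unknown and lies between 0% and 100%.

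- Stated interest, 60% afterwards: 60 − 100 = -40 to 60 − 0 = +60 points. If interest did not fall, 0 to +60.
- Enrolment, 120 of 400 = 30%: 30 − 100 = -70 to +30 points. If education did not reduce enrolment, 0 to +30.

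**3. Whether sample size helps.** The 95% half-width for 60% is 1.96 × √(0.6 × 0.4/n): 4.8 points at n = 400 and 3.0 at n = 1,000. Enrolling more people sharpens the post-visit level but leaves the ranges in step 2 unchanged.

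**4. The sign-up count.** Each outside or duplicate sign-up adds 1/n to apparent uptake. Twenty add 20/400 = 5 points (20% would read as 25%) or 20/1,000 = 2 points.

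**5. The advanced-disease question.** Suppose 120 of 400 sign up and A participants have advanced disease. Uptake in that group lies between max(0, 120 − (400 − A))/A and min(120, A)/A. For A = 20, 40 or 80 this is 0% to 100%. The aggregate count says nothing about the group the question names.

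**6. What an optional paired question could detect.** This concerns stated interest, not enrolment. McNemar test, normal approximation, n = 400, with u moving to interested, v moving away, d = u − v and s = u + v: power = Φ[(d√n − 1.96√s)/√(s − d²)].

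- u = 10%, v = 5%: (1.000 − 0.759)/0.384 = 0.627, power 0.735.
- u = 15%, v = 5%: (2.000 − 0.877)/0.436 = 2.577, power 0.995.

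A 10-point net change would be detected reliably and a 5-point net change less so, under these assumed rates.

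**The case against.** The strongest reply is that these aims are descriptive. The questions ask what portion of patients will do something, the protocol calls the results baselines because nothing comparable exists, and the SAP confines the likelihood items to frequencies. On that reading, efficacy is a loose word for uptake. The text also speaks of participants who enrol after the test, so the intended numerator is clear even if its mechanism is not.

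Much of this stands. The post-visit level of interest is estimable and useful as a baseline, and rewording alone removes the effect claim. It does not excuse the present wording, which says that efficacy will be measured and effectiveness can be shown. A descriptive uptake share still needs a defined numerator, and the advanced-disease question still needs a split by stage.

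The reply is also right about a before-and-after question:

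- The survey follows the scan result, so a paired change mixes education with that result.
- It would measure stated interest, not enrolment, which is the outcome in the efficacy sentence.
- The intake form in Step 2 follows the liver-disease explanation in Step 1, so no item on it precedes all education.

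For these reasons the question is optional and its result must be labelled accordingly.

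**Conclusion.** The concern holds in a limited form. The design yields a post-visit level of interest and, once the count is secured, of uptake. It cannot show efficacy or effectiveness at any sample size. The size of the gap depends on the assumed post-visit level: -40 to +60 points at 60%, with 0 to +60 resting on the further assumption that interest did not fall. The sign-up count lacks a stated rule for eligibility, uniqueness and stage.

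Four stronger readings are tempting but not supported:

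- *That uptake will be inflated by outsiders.* The documents do not say that the online tools are open to the public, and the outreach they describe concerns obesity and liver disease. The 20 extra sign-ups are hypothetical.
- *That a diet item was dropped from the survey.* The SAP says "We will calculate the frequency of answers for each of the five items reflecting subjects' likelihood of" and lists four, as does the survey, with an empty fifth bullet in the SAP. This is a clerical mismatch. Nothing suggests the fifth was a diet item, and diet uptake is planned as a count of behaviour.
- *That the likelihood rating is the only individual information on trial education.* Question 3 of the survey also has a checkbox on whether the discussion of trials was useful. It too is completed after the visit, so it supplies no reference value.
- *That the main result is compromised.* The primary FibroScan outcome does not depend on any of this.

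**What to change.** 1. **Wording.** In Hypothesis and Questions Posed by this Study, replace *efficacy* and *effectiveness* with *post-visit uptake and stated interest (descriptive)*. This costs only the edit and settles the effect claim on its own.

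2. **Count.** Print a one-time, non-identifying code on the handout given in Step 4, carrying only a disease-stage marker. Count unique codes used and divide by the number screened, overall and by stage. Add this analysis to the SAP and state which stages count as advanced. The cost is a set of printed codes, a code field at sign-up and a sentence in Confidentiality. Codes should be tallied apart from any contact details entered at sign-up, so that stage is not joined to a person.

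3. **Optional paired item.** Add a trial-interest item, and a diet-support item if wanted, to the Step 2 intake form. Have it completed before any trial or diet information is given, and repeat it in the post-test survey under the same study ID code. Report the paired change as change over the whole visit (education plus scan result), not as an education effect or an effect on enrolment. The cost is two form lines and the ID code on the survey. Trial and diet messages and literature must be held back until the form is done, and asking beforehand may slightly raise interest.

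The SAP's five-versus-four item count can be corrected in the same edit.
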